## 10.5. EEsAI Score

The tables and fomular below are used to calculate the EEsAI score.

Weekly EEsAI score

| Item                            | Score (total
set to 100) |
|---------------------------------|-----------------------------|
| Frequency of trouble swallowing |                             |
| Never                           | 0                           |
| 1–3 times/wk                    | 15                          |
| 4–6 times/wk                    | 27                          |
| Daily                           | 31                          |
| Duration of trouble swallowing  |                             |
| <=5 min                         | 0                           |
| >5 min                          | 6                           |
| Pain when swallowing            |                             |
| No                              | 0                           |
| Yes                             | 15                          |
| VDQ score                       |                             |
| 0                               | 0                           |
| 0.1–2.5                         | 12                          |
| 2.6–5.0                         | 19                          |
| 5.1–7.5                         | 21                          |
| 7.6–10.0                        | 23                          |
| AMS score                       |                             |
| 0                               | 0                           |
| 0.1–2.5                         | 0                           |
| 2.6–5.0                         | 0                           |
| 5.1–7.5                         | 9                           |
| 7.6–10.0                        | 25                          |
| Total                           | 100                         |

Daily EEsAI score

| Item                            | Score (total
set to 100) |
|---------------------------------|-----------------------------|
| Frequency of trouble swallowing |                             |
| Never                           | 0                           |
| Present                         | 11                          |
| Duration of trouble swallowing  |                             |
| <=5 min                         | 0                           |
| >5 min                          | 14                          |
| Pain when swallowing            |                             |
| No                              | 0                           |
| Yes                             | 6                           |
| VDQ score                       |                             |
| 0                               | 0                           |
| 0.1–2.5                         | 1                           |
| 2.6–5.0                         | 17                          |
| 5.1–7.5                         | 27                          |
| 7.6–10.0                        | 51                          |
| AMS score                       |                             |
| 0                               | 0                           |
| 0.1–2.5                         | 0                           |
| 2.6–5.0                         | 0                           |
| 5.1–7.5                         | 2                           |
| 7.6–10.0                        | 18                          |
| Total                           | 100                         |

1. VDQ score - one should get a number from 0 to 10.

$$VDQ = 10 * (N1 * 1 + N2 * 2 + N3 * 3) / (D * 3)$$

Where:

1. N1 = number of food consistencies graded with 'Mild difficulties'
2. N2 = number of food consistencies graded with 'Moderate difficulties'
3. N3 = number of food consistencies graded with 'Severe difficulties'
4. D = number of relevant food consistencies (different than 'Not applicable')

2. AMS score - one should get a number from 0 to 10.

$$AMS = 10 * (N1 * 1 + N2 * 2 + N3 * 3 + N4 * 5) / (D * 5)$$

Where:

1. N1 = number of food consistencies with 'Yes' to 'Eating slowly' only
2. N2 = number of food consistencies with 'Yes' to 'Modification' only
3. N3 = number of food consistencies with 'Yes' to both 'Eating slowly' and 'Modification'
4. N4 = number of food consistencies with 'Yes' to 'Avoidance' only
5. D = number of relevant food consistencies (different than 'Not applicable')

## 10.6. Medication for RESCUE TREATMENTS

The medications given post-baseline are considered rescue Medication.

| Therapeutic Class                     | Chemical Class                   |  |
|---------------------------------------|----------------------------------|--|
| ANTINEOPLASTIC AGENTS                 | MONOCLONAL ANTIBODIES            | Check if patient took Omalzumab (Anti IgE) |
| CORTICOSTEROIDS FOR SYSTEMIC USE      | GLUCOCORTICOIDS                  | Except route of administration as topical  |
| DRUGS FOR ACID RELATED DISORDERS      | PROTON PUMP INHIBITORS           |  |
| DRUGS FOR OBSTRUCTIVE AIRWAY DISEASES | GLUCOCORTICOIDS                  | Except route of administration as topical  |
| DRUGS FOR OBSTRUCTIVE AIRWAY DISEASES | LEUKOTRIENE RECEPTOR ANTAGONISTS |  |
| IMMUNOSUPPRESSANTS                    | INTERLEUKIN INHIBITORS           | Check if patient took Anti IL5             |

Signature Page for VV-RIM-00013092 v1.0

|          |   |
|----------|---|
| Approval | 
[REDACTED]
14-Apr-2017 14:10:58 GMT+0000 |
|----------|---|

|          |   |
|----------|---|
| Approval | 
[REDACTED]
14-Apr-2017 14:14:21 GMT+0000 |
|----------|---|

|          |   |
|----------|---|
| Approval | 
[REDACTED]
14-Apr-2017 17:27:40 GMT+0000 |
|----------|---|

Signature Page for VV-RIM-00013092 v1.0 Approved

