### 4.3. Pre-treatment/ Concomitant Medications and Procedures

Medications/Procedures will be recorded from the day of informed consent until the EOS visit. Medications will be coded to the ATC level 2 (therapeutic main group) and ATC level 4 (chemical/therapeutic subgroup), according to the latest available version of WHO Drug Dictionary (WHODD) version Sep 2016 at the coding of CRO. Patients will be counted once in all ATC categories linked to the medication.

Pre-treatment medications/procedures: medications taken or procedures performed prior to administration of the first study drug.

Concomitant medications/procedures: medications taken or procedures performed following the first dose of study drug through the EOS visit.

Prohibited concomitant medications/procedures during week 12 treatment period Treatment with the following concomitant medications is prohibited:

- Medications used for the treatment of EoE .
- Allergen immunotherapy.
- Patients who are not using PPI in the 8 weeks prior to screening cannot start PPI therapy prior to EOT visit
- Treatment with a live (attenuated) vaccine
- Treatment with an investigational drug (other than dupilumab)

Treatment with the following concomitant procedures is prohibited:

- Major elective surgical procedures
- Esophageal dilation (considered rescue procedure)
- Diet change.

If medically necessary (eg, for treatment of intolerable EoE symptoms) patients may be rescued with a prohibited medication or procedure at the discretion of the investigator. Patients who receive rescue treatment with a prohibited medication or procedure through week 12 will be permanently discontinued from study drug.

Rescue treatments for EoE: Blinded adjudication of rescue treatments will be implemented before database locks by considering the type of medications. A predetermined algorithm for rescue medications listed in [Appendix 10.6](#) will be used to programmatically search the concomitant medications (CMs). The rescue CMs will be reviewed and adjudicated by the medical monitor in a blinded fashion.

All patients will complete the schedule of study visits and assessments whether or not they complete study treatment. Investigators should make every attempt to conduct efficacy and safety assessments immediately before administering any rescue treatment. An unscheduled visit may be used for this purpose if necessary.

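### Appendix 10.6 classes any PPI given post-baseline as rescue, with no new-start condition, which conflicts with the narrower PPI prohibition and the description of rescue in Section 4.3

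*SAP*

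**What the plan says.** **Rescue list.** Appendix 10.6 opens with "The medications given post-baseline are considered rescue Medication" and then gives six rows by therapeutic and chemical class. One row is "PROTON PUMP INHIBITORS", and its third column is empty. Four of the other five rows carry a restriction there, either on route or on a specific drug to check.

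**PPI prohibition.** Section 4.3 limits PPI use in one bullet: "Patients who are not using PPI in the 8 weeks prior to screening cannot start PPI therapy prior to EOT visit".

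**What is searched.** Section 4.3 defines concomitant medications as "medications taken or procedures performed following the first dose of study drug through the EOS visit". The Appendix 10.6 list is run by program on those records.

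**How hits are judged.** Section 4.3: "Blinded adjudication of rescue treatments will be implemented before database locks by considering the type of medications". It adds: "The rescue CMs will be reviewed and adjudicated by the medical monitor in a blinded fashion".

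**What rescue is elsewhere.** Section 4.3 says that, if medically necessary, "patients may be rescued with a prohibited medication or procedure at the discretion of the investigator", and that "Patients who receive rescue treatment with a prohibited medication or procedure through week 12 will be permanently discontinued from study drug". Section 2.3 also stops study treatment after rescue. Section 5.7.1 refers to data collected after rescue was initiated.

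**The concern.** The rule that decides who was rescued is wider than the SAP's own idea of rescue. A patient who took a PPI before screening and continues it breaks no PPI rule in Section 4.3. That patient is still taking a listed drug after baseline, so the search finds the record, and the adjudication basis named in the SAP gives no reason to reject it.

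Rescue status drives several results:

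- Continuous endpoints: data after rescue are set to missing and imputed (Sections 5.7.1 and 5.7.2).
- Responder endpoints for SDI and EEsAI: the patient is a non-responder (Sections 5.7.1 and 5.7.3).
- Rescue use through week 12, itself a secondary endpoint: the patient counts as an event (Section 4.4.2).

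A patient on stable background therapy could therefore lose valid data and be recorded as a treatment failure.

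**Working it through.** **1. The texts side by side**

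| Question | Appendix 10.6 and the adjudication sentence of 4.3 | Rest of the SAP |
|---|---|---|
| Which PPI use counts? | Any given post-baseline | Only a new start in a recent non-user is prohibited (4.3) |
| Must rescue be a prohibited drug? | Not stated | Yes (4.3) |
| Must it be newly begun? | Not stated | Section 5.7.1 speaks of rescue as initiated |
| Does study drug stop? | Not stated | Yes (2.3, 4.3) |
| Basis for review | Type of medication | No start-date or prior-use rule for rescue |

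A continued PPI satisfies the left column and fails the right. A continued PPI and a new one are of the same type, so the named basis cannot separate them. Start date, dose, indication and prior use can.

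**2. Imputed dates do not solve it.** Section 6.3 imputes concomitant medication start dates by the AE start-date rule. If the year is missing, or only the year is known and equals the first-dose year, the start becomes the first-dose date unless the end date is earlier. A PPI begun before the study with a partial date can then look as if it began on day 1.

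**3. Which analyses are protected.** Sensitivity analyses 1 and 4 in Section 5.7.2 keep data after rescue, for the primary endpoint only. Analyses 2 and 3 carry post-baseline values forward, but a patient treated as rescued from day 1 has none to carry. Appendix 10.1 enters no supportive method for secondary continuous variables and leaves that cell blank for categorical ones. Biopsies and EoE-EREFs have one planned on-treatment assessment, at week 12, so an upheld hit removes the only planned value.

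**4. Size per patient.** Input: 22 enrolled per arm (Section 2.2). One upheld hit in a patient not otherwise rescued adds 1/22 = 4.5 points to that arm's rescue-use percentage. If the patient is a true responder, the arm's responder percentage falls by the same 4.5 points. Two hits give 2/22 = 9.1 points and four give 4/22 = 18.2.

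**5. Primary endpoint, worst case.** Inputs from Section 2.2: difference 3, SD 2.46, two-sided 5%, 18 evaluable per arm. Power comes from the noncentral t distribution with 2n − 2 degrees of freedom and noncentrality 3 / (2.46 × √(2/n)).

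The SAP's figure first: at n = 18 the noncentrality is 3.659, the critical value with 34 degrees of freedom is 2.032, and power is 94.4%, matching the stated 94%. Enrolment also reproduces: 18 / 0.85 = 21.2, rounded up to 22.

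Now assume that k continuing users per arm are upheld as rescued, with all their post-baseline SDI lost and nothing recovered by imputation. The SAP gives no PPI rate, so k is an assumed range.

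| k per arm | n left per arm | Power |
|---|---|---|
| 0 | 18 | 94.4% |
| 1 | 17 | 93.1% |
| 2 | 16 | 91.6% |
| 4 | 14 | 87.4% |

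**The case against.** The strongest reply is that Appendix 10.6 is a search list and not the final classification. A broad search followed by blinded review is ordinary practice, and the rows that tell the reader to check for a specific drug read as prompts for a reviewer. The SAP elsewhere describes rescue as a prohibited treatment given when medically necessary, followed by stopping study drug. Under the literal rule every continuing PPI user would have to stop on day 1, which the authors cannot have meant. The adjudication sentence does not say that type is the only consideration. Section 5.3 plans to list indication, onset day, dose and ongoing status, so most of the information needed to separate the cases is planned.

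Much of this stands. A reader might infer that the trial will count all continuing PPI users as rescued. The documents do not support that, because the monitor has good grounds to reject such hits.

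It is also true that the SAP nowhere says outright that continued PPI is allowed. That is inferred from the PPI bullet, alongside a general bar on medications used to treat EoE. The inference is reasonable, since a bullet limited to recent non-users would serve no purpose if all PPI use were barred.

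What the reply does not supply is the criterion. The passages show an intent at odds with the wording of Appendix 10.6, and none tells the monitor to use start date or prior use to decide rescue.

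**Conclusion.** The point holds as a conflict within the SAP. The written rescue rule for PPIs is wider than the prohibition and the description of rescue that it is meant to serve, and the stated adjudication basis cannot close the gap. It should be corrected, but harm is possible and not shown.

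The size is unknown. The SAP gives no rate of background PPI use, and adjudication will probably remove most such hits. The exposure lies mainly in the secondary endpoints, at about 4.5 points per upheld patient per arm, because they have no analysis that ignores rescue.

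A reader might infer from the power table that the primary analysis is in danger; losing half of the 18 evaluable patients per arm would give 68.1%. The documents do not support that conclusion. It would require many continuing users, every hit upheld, equal loss in both arms and no recovery by imputation, and two of the primary sensitivity analyses keep data after rescue. The likely effect on the primary endpoint is small, and the stated 94% power and 22 per arm are not in question.

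**What to change.** Change two places, the PPI row of Appendix 10.6 and the adjudication sentence of Section 4.3:

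- A PPI is a rescue candidate only if, after the first dose and through week 12, it is newly started, restarted, or increased in dose for EoE symptoms.
- A PPI continued at a stable pre-baseline dose is not rescue.
- The blinded medical monitor decides on recorded (not imputed) start date, dose, indication and prior PPI use, as well as type of medication.

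Restarts and dose increases need to be named. A rule limited to new starts in recent non-users would never count a prior user whose PPI was restarted or raised for worsening symptoms, and would keep data affected by that rescue.

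The cost is two lines of SAP wording, applied at an adjudication already planned before database lock, and a few data queries where a PPI start date or dose is incomplete. Sample size and the primary model do not change.
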